# Study Protocol

Behavioral Mechanism of Energy Compensation with Exercise  
NCT04651218

October 13, 2022

Visit 1 (week 1). The Study Coordinator will meet with each participant for a 30-minute orientation session. At this time, participants will have the study explained, questions answered, complete the necessary screening questionnaires (health history, PAR-Q+), complete an Accu-Check blood glucose test, and, if deemed eligible and interested, sign the informed consent. Upon enrollment, participants will also complete a food frequency questionnaire (DHQ-3), be assessed for body composition (BodPod), and have waist circumference measured. Participants will also be provided an ActiGraph accelerometer to objectively assess physical activity for the next seven days and scheduled for Visit 2 at least eight days later. Participants will be instructed not to purposely change dietary behaviors while enrolled in the study (i.e. start to diet).

Visits 2 and 3 (week 2 and 3). On the day of Visit 2, participants will record the specific foods, quantities, and time of day they consumed them prior to their testing visit. Participants will be instructed to eat the same foods at the same time of day prior to Visit 3 as they did prior to Visit 2. Visit 2 and 3 will be scheduled at the same time of day on the same day of the week where participants will be able to practice "usual" dietary behaviors, i.e. not on a holiday or a special occasion. Upon arriving to the LHBP exactly four hours post-prandial in the afternoon, participants will complete assessments for food reinforcement, attentional bias and inhibitory control for food cues before and twice after an acute bout of either exercise or sedentary activity, with one visit featuring exercise and the other visit featuring a sedentary activity. The order of the visits will be counterbalanced. Visual analog scales (VAS) will be performed for hunger and exercise enjoyment prior to each set of assessments. For female participants, these visits will occur while in the follicular phase, which will be assessed by a menstrual cycle questionnaire. Participants will wear the accelerometer to record physical activity during the washout period between assessment visits and be instructed to remain sedentary.

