Statistical analysis plan

Behavioral Mechanism of Energy Compensation with Exercise
NCT04651218

October 13, 2022

Statistical Analysis Linear mixed models will be fit with exercise and time as random effects to account for repeated measures and sex as a fixed effect. Response variables will be transformed if appropriate. With binary explanatory variables, an unstructured covariance matrix for the random effects will be assumed, but alternatives will be considered if needed. VAS scale ratings of hunger/satiety and exercise enjoyment will be assessed and included for adjustment as necessary. Power analysis: Because of our three response variables, we will use a Bonferroni corrected type I error rate of $0.05/3 = 0.017$ for our regression models. In a linear regression model with $n = 60$, 30 males and 30 females, counterbalanced to start with and without exercise and then crossing over to the other treatment, we will have 80% power to detect models with R squared of 20.4% or more (nQuery 8.5.1). Our mixed models will improve model fit and decrease variance estimates compared with linear regression, thus increasing power or decreasing R squared type measures that can be detected.

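### Adding one sex-by-exercise term would be a cheap improvement: sex as a main effect adds essentially no precision to the exercise contrast and cannot show whether men and women respond differently

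*SAP*

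**What the plan says.** The Statistical Analysis paragraph of the SAP reads "Linear mixed models will be fit with exercise and time as random effects", the random terms being there "to account for repeated measures and sex as a fixed effect". That is the only place where sex appears as a model term. The power paragraph of the SAP plans for "30 males and 30 females, counterbalanced to start with and without exercise and then crossing over to the other treatment". It also says "we will use a Bonferroni corrected type I error rate of" 0.05/3 = 0.017, for three response variables, and gives 80% power for a whole-model R squared of 20.4%.

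The Protocol, under Visits 2 and 3, puts every participant through both conditions, "with one visit featuring exercise and the other visit featuring a sedentary activity", with assessments "before and twice after an acute bout of either exercise or sedentary activity". Its only sex-specific provision is to schedule women's visits in the follicular phase. Neither document names an interaction with sex, a sex-specific estimate or an objective about sex differences.

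**The concern.** In a two-condition crossover each person is their own control. Sex does not change between the two visits, so a sex main effect raises or lowers both of a person's visits equally and vanishes from their difference. Its coefficient describes only whether men and women differ on average across all six assessments.

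Two consequences follow if no interaction is fitted. First, any sex difference in the response to exercise is treated as unexplained person-to-person variation in the exercise effect, which widens the standard error of the average effect. Because the 30/30 split is fixed by design, that part of the variation is not sampling error in the average and need not be paid for. Second, the plan has no estimate of the sex difference, and a sex-by-exercise result reported later would be unplanned.

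**Working it through.** **Inputs.** From the SAP: n = 60, 30 men and 30 women, two-condition crossover, alpha 0.05/3, 80% power, R squared 20.4%. From the Protocol: both conditions in every participant, three assessments per visit. Assumed: two-sided tests, complete pairs, a fixed exercise effect, and one exercise-minus-sedentary contrast per person with within-sex SD 1. The documents give no sex difference in response, so d is shown over a range.

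**1. The plan's own figure.** For the overall F test in a linear regression with k predictors, lambda = n·R²/(1 − R²) = 60 × 0.204/0.796 = 15.4, with k and 60 − k − 1 degrees of freedom. At alpha 0.05/3 the smallest R squared with 80% power is 15.5% for k = 1, 18.4% for k = 2, 20.4% for k = 3 and 22.1% for k = 4. The figure reproduces with three predictors (power 79.9% at R squared 20.4%). The SAP does not list them. Exercise, sex and a one-degree-of-freedom time term make three; so do exercise, sex and their product. Exercise, sex and a three-level time factor make four, which does not match.

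**2. Cancellation.** Write Y = b0 + bS·sex + bE·exercise + person effect + error. Within a person, exercise minus sedentary is bE plus error; bS has gone. In one simulated 60-person trial (two conditions, three assessments, 30/30 by sex), the exercise estimate was 0.10216 with SE 0.13672 whether or not sex was in the model, although the sex coefficient was 1.32.

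**3. Standard error.** Let the exercise effect be μ + d/2 in one sex and μ − d/2 in the other. Around a common mean, the variance of the person-level differences is 1 + d²/4. The reported SE is then sqrt((1 + d²/4)/60) instead of sqrt(1/60) = 0.129, a ratio of sqrt(1 + d²/4).

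**4. Power for the average effect.** Take μ = (2.394 + 0.842) × 0.129 = 0.418 SD, the 80% point by normal approximation at 0.05/3; the t-test gives 78%. Simulated power:

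| d | SE ratio | Power without interaction | Power with interaction |
|---|---|---|---|
| 0 | 1.000 | 78% | 78% |
| 0.5 | sqrt(1.0625) = 1.031 | 75–76% | 78% |
| 0.84 | sqrt(1.1764) = 1.085 | 71% | 78% |
| 1.0 | sqrt(1.25) = 1.118 | 68% | 78% |

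At d = 0.2 and 0.3 the loss is about 0 and 1 point.

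**5. What the interaction can show.** The SE of the sex difference is sqrt(1/30 + 1/30) = 0.258, twice 0.129. By exact t with 58 degrees of freedom, 80% power needs a sex difference of 0.86 SD at alpha 0.05/3 or 0.74 SD at 0.05. The average effect needs 0.43 SD (exact t, 60 pairs). A sex difference of 0.43 SD would have about 22% power at 0.05/3; one of 0.5 SD would have 31%, or 48% at alpha 0.05.

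**The case against.** The strongest reply is that nothing the trial sets out to answer is left unanswered. No sex-difference aim is stated, and follicular-phase scheduling treats sex as variation to control. A balanced split is useful without an interaction: with complete data the pooled effect already is the equally weighted average of the two sexes. All of this stands. A reader might infer from "30 males and 30 females, counterbalanced to start with and without exercise" that the trial was designed to compare the sexes and then failed to analyse its own question. The documents do not say so; this is an analysis that could be had cheaply, not a contradiction.

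The absence of an interaction is also read from silence. Step 1 shows that the three unlisted predictors could include the sex-by-exercise product. Sex as a main effect only is the plain reading, not a certain one, and it is a reason to list the fixed terms.

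Read literally, the SAP gives exercise only as a random effect, so there would be no mean exercise effect to sharpen. That is a separate and more basic gap, on which this point depends.

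A reader might further infer that the sex term can never alter the exercise result. That is too strong. When 20 of 60 simulated participants lost one visit, adding sex moved the baseline exercise estimate from 0.188 to 0.124, though the SE fell only from 0.16116 to 0.16085, about 0.2%. The SAP's optional adjustment for hunger and enjoyment ratings can also make cancellation inexact. What survives is the statement about precision.

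Finally, the harm is conditional. Losses of 7 to 10 points need d of 0.84 to 1.0, at least twice the average effect used here. The error is conservative: a wider SE, without bias or excess false positives.

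**Conclusion.** The point holds as a cheap improvement. On the plain reading of the SAP, and with complete pairs, the sex main effect adds essentially no precision to the exercise contrast and gives no information on differential response. Omitting the interaction costs nothing at d = 0, about 2 points of power at d = 0.5 and about 10 points at d = 1.0, through an SE too wide by 3% and 12%. These sizes assume a fixed exercise effect, a single person-level contrast, two-sided 0.05/3 and a true average effect of 0.418 SD; which d applies is unknown.

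It would be wrong to conclude that the planned exercise result is invalid or biased, or that the 30/30 split is at fault. The average effect is validly estimated without the term, and the limit lies in the model. Nor could the trial settle a sex difference once the term is added: only one of about 0.86 SD or more (0.74 SD at alpha 0.05) would be detected with 80% power.

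**What to change.** In the SAP:

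- List the fixed terms, with exercise among them.
- Add one sex-by-exercise fixed term or, if the tested quantity is a change from the pre-bout assessment, the interaction of sex with that exercise-by-assessment contrast.
- Define the result tested at 0.05/3 as the exercise effect averaged with equal weight on men and women. Coding sex as −½ and +½ makes the exercise coefficient this average; with 0/1 coding it would be the effect in the reference sex.
- Report the effect in each sex and their difference with confidence intervals, as secondary estimates labelled exploratory, and make no confirmatory sex claim.

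The cost is SAP wording and about one degree of freedom, with no new data or visits. The real downside is a set of imprecise sex comparisons over three outcomes without error control. This is why only one interaction term is proposed and why the results should be presented as estimates, not tests.

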Acute Bout of Exercise. Participants will complete assessments of food reinforcement, attentional bias and inhibitory control before and after an acute bout of exercise during Visit 2 or visit 3 (depending on counterbalanced order). Participants will be provided a Polar A-300 heart rate monitor with smart-cal™ technology that factors the individual's sex, age, weight, activity level, and heart rate to produce an estimate of total energy in kilocalories (kcal) expended during the exercise session, with kcal expended displayed in real- time. Participants will engage in exercise on an elliptical ergometer (Octane Fitness ZR8) for the amount of time it takes them to expend 500 kcal

under supervision of a researcher in the laboratory. Participants will exercise at a self-selected intensity of at least 65% heart rate reserve (HRR), an intensity commonly prescribed for sedentary individuals beginning an exercise program. Based on previous studies conducted in our lab, 500 kcal of energy expenditure is attainable for even the most sedentary individual with exercise sessions lasting between 30 and 70 minutes depending on body mass and intensity of exercise. Prescribing the exercise bout on energy expenditure rather than duration or intensity will standardize the amount of total work being done across all participants. While both the intensity and duration of the exercise could be controlled, due to differences in body mass of the participants, either the exercise time or total work would still vary. An energy expenditure of 500 kcal is specifically used to ensure the exercise bout is of sufficient volume (intensity \* time) to produce weight loss if included in a long-term program and to elicit a dopaminergic response. Participants will be permitted to drink 0.5 l of water during and after the exercise bout. Participants will take a brief 15-minute rest after completing the exercise session before repeating assessments for food reinforcement, attentional bias and inhibitory control for food cues (post exercise assessment 1). Participants will repeat these assessments 60 minutes after cession of the exercise and sedentary activity bout (post exercise assessment 2).

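### The SAP models no visit-specific bout response, so with independent residuals the standard error of the exercise-minus-TV difference in pre-to-post change can be too small

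*SAP*

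**What the plan says.** The protocol (Visits 2 and 3) has food reinforcement, attentional bias and inhibitory control assessed "before and twice after an acute bout of either exercise or sedentary activity", with exercise at one visit and TV at the other. Under Acute Bout of Exercise, the first post-bout set follows a 15-minute rest and the second comes 60 minutes after the bout ends. Each outcome therefore has six values per participant, in a layout of two visits by three assessments.

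The SAP (Statistical Analysis) states: "Linear mixed models will be fit with exercise and time as random effects to account for repeated measures and sex as a fixed effect". On covariance it adds that "an unstructured covariance matrix for the random effects will be assumed, but alternatives will be considered if needed". That sentence concerns the random effects only. The SAP gives no residual covariance, no fixed or random exercise-by-time term, no before-to-after contrast and no coding of time. It does speak of binary explanatory variables, which suggests before/after coding.

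On the error rate: "we will use a Bonferroni corrected type I error rate of $0.05/3 = 0.017$ for our regression models".

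**The concern.** A pre-bout assessment is there to measure change, and the TV visit is there to compare that change. The natural target is therefore (mean post − pre, exercise day) minus (mean post − pre, TV day).

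A participant's intercept cancels within each visit's change, and so does that participant's exercise effect. The time effect cancels between visits. Nothing in the named random-effects structure remains in this contrast, so its standard error rests on the residual alone. If a participant responds more strongly than usual to one day's bout, both post-bout values of that visit carry the deviation. A model with independent residuals counts them as two separate pieces of information. Making the random-effects covariance unstructured does not help, because it governs only terms that cancel.

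At stake are intervals that are too narrow for this contrast and a test that rejects more often than the Bonferroni level allows.

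**Working it through.** **The plan's own figure.** The SAP claims 80% power for a model R squared of 20.4% with n = 60. The number of predictors is not stated; three is assumed here. For the overall F test, the noncentrality is 60 × 0.204/0.796 = 15.38 on 3 and 56 degrees of freedom. Power is 80.1% at alpha 0.017 and 79.9% at 0.05/3, so the figure reproduces. It comes from a linear regression, uses no within-visit correlation, and is unaffected by this point.

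**Inputs**
- From the documents: 60 participants, two visits, three assessments per visit, alpha 0.05/3 = 1.67%.
- Assumed: random effects at participant level including an intercept; independent residuals; complete data.
- Not in the documents, so shown as a range: ρ, the correlation between the two post-bout values of a visit given the random effects. With residual variance s² and visit-specific bout-response variance w² (shared by both post-bout values), ρ = w²/(w² + s²). Any part of the response common to both visits goes into the random time effect and is not counted here.

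**True variance of the contrast, per participant.** Each visit contributes s² + s²/2 + w², so the two together give 3s² + 2w².

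**Variance the model reports.** The contrast has squared coefficients summing to 3, so the model reports 3 times its pooled residual variance.
- Three-level time: the residual pools two directions, the contrast itself (s² + 2w²/3 after scaling) and the between-visit difference in post 1 to post 2 change (s²). The average is s² + w²/3, and the model reports 3s² + w².
- Before/after time: the residual pools three directions, the contrast and the post 1 to post 2 difference within each visit. The average is s² + 2w²/9, and the model reports 3s² + 2w²/3.

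**Numbers.** Set s² + w² = 1. The true variance is 3 − ρ, and the model reports 3 − 2ρ (three-level) or 3 − 7ρ/3 (before/after). The SE ratio r is the square root of model over true variance. Actual type I error is 2 × [1 − Φ(2.394 r)], where 2.394 is the two-sided normal critical value for 0.05/3.

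| ρ | True | Model, 3-level | r | Type I | Model, before/after | r | Type I |
|---|---|---|---|---|---|---|---|
| 0 | 3.0 | 3.0 | 1.000 | 1.67% | 3.0 | 1.000 | 1.67% |
| 0.3 | 2.7 | 2.4 | 0.943 | 2.4% | 2.3 | 0.923 | 2.7% |
| 0.5 | 2.5 | 2.0 | 0.894 | 3.2% | 1.833 | 0.856 | 4.0% |
| 0.7 | 2.3 | 1.6 | 0.834 | 4.6% | 1.367 | 0.771 | 6.5% |

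**Check by fitting.** At ρ = 0.5 and n = 60 the formulas give a true SE of √(2.5/60) = 0.204, and model SEs of √(2.0/60) = 0.183 (three-level) and √(1.833/60) = 0.175 (before/after). REML mixed-model fits to simulated data agree. One small set gave a mean model SE of 0.184 against 0.207 from the per-participant contrast. Another gave 0.175 against 0.202.

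**Contrasts that behave differently**
- Exercise averaged over all three assessments keeps its own random effect, so its SE is unaffected. That average includes the pre-bout score.
- The between-visit difference in post 1 to post 2 change has true variance 4s², while the model reports 4 times the pooled residual. At ρ = 0.5 its SE is too large, by a factor √(1 + 1/3) = 1.15 (pooling as for three-level time) or √(1 + 2/9) = 1.11 (pooling as for before/after time).
- With AR(1) residuals within a visit (0.3 and 0.6) in place of a shared response, the target contrast still has too small an SE: ratios 0.957 and 0.926 with three-level time, 0.943 and 0.900 with before/after time. The exercise-visit change from pre to first post has an SE that is slightly too large (1.021 and 1.038).

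**Effect of the remedy.** Adding a random exercise-by-time (before/after) effect brought the ratio for the target contrast to 1.000 in every scenario computed.

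**The case against.** The strongest reply is that the SAP never defines the contrast whose standard error is criticised. It lists sex as the only fixed effect and names no exercise-by-time term. It also fixes no residual structure: independence is a common software default, not a documented choice, and the clause about alternatives leaves room for another model. Nor is independence given the random effects an error in itself, since those effects already correlate a participant's assessments.

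All of this stands, and it limits the point to a conditional one. It does not remove it. The clause on alternatives concerns the random-effects covariance and names neither a trigger nor a replacement, so it is not a safeguard. Leaving the design's natural contrast undefined is a companion gap in the same paragraph, and the same edit should close it.

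A reader might infer that the trial's standard errors are bound to be too small. The documents do not support that: they give no variance components, the shortfall is zero at ρ = 0, and some contrasts err the other way. For the simple change within the exercise visit, the shortfall was only about 2% to 9% when w² ranged from 0.25 to 2 times s², under further assumed variances. A reader might also turn the per-outcome error rates into a family-wise rate. That needs the correlation among the three outcomes, which the documents do not give and which is unlikely to be zero when all three are measured in the same sessions.

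**Conclusion.** The point holds in conditional form. Fitted as written with default residuals, the SAP's model gives too small a standard error for the exercise-minus-TV difference in pre-to-post change whenever bout responses vary by visit. Over ρ = 0.3 to 0.7 the SE is 6% to 17% too small with three-level time and 8% to 23% too small with before/after time. The test then runs at about 2.4% to 6.5% in place of 1.67%. The size rests on an assumed ρ, participant-level random effects with an intercept, independent residuals and complete data. This is a cheap improvement to the analysis plan. It does not show that the planned analysis must fail, and it does not touch the stated power figure.

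**What to change.** In the SAP:
- Name exercise, time and exercise-by-time as fixed effects, alongside sex, and state how time is coded.
- Name (mean post − pre, exercise day) minus (mean post − pre, TV day) as the target contrast for each outcome.
- Add a participant-level random exercise-by-time (before/after) effect. Alternatively, replace the random effects with an unstructured covariance over the six visit-by-assessment cells, using Kenward-Roger degrees of freedom.
- State the fallback if the model does not converge: compute the target contrast once per participant and analyse it across the 60 participants. In simulation this held its error rate at 1.5% to 1.8%.

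The cost is wording only; no visit or measurement changes. Where ρ is positive, the correct intervals are wider by the reciprocal of the ratios above: about 6%, 12% and 20% with three-level time, or 8%, 17% and 30% with before/after time, at ρ = 0.3, 0.5 and 0.7. There are also more covariance parameters to estimate. The six-cell unstructured matrix has 6 × 7/2 = 21 from 60 participants, which is why the random-effect version and the fallback should be written down in advance.

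### Bonferroni across the three outcomes is valid, but Holm's step-down test at the same 5% family-wise error rejects at least as much and is a cheap improvement

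*SAP*

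**What the plan says.** The only multiplicity rule is in the SAP's Statistical Analysis paragraph, under the run-in label for the power analysis: "Because of our three response variables, we will use a Bonferroni corrected type I error rate of $0.05/3 = 0.017". The sentence goes on to apply this rate to the regression models, so it is worded as a rule for testing, not only for sample size. The stated reason is the number of outcomes. The SAP does not name the three. The Protocol does, under Visits 2 and 3: "assessments for food reinforcement, attentional bias and inhibitory control for food cues".

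The power statement uses the same threshold. It starts "In a linear regression model with $n = 60$, 30 males and 30 females" and concludes "we will have 80% power to detect models with R squared of 20.4% or more (nQuery 8.5.1". It comes from ordinary regression, and the SAP expects the planned analysis to do better: "Our mixed models will improve model fit and decrease variance estimates compared with linear regression".

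Neither document mentions a step-down, hierarchical or gatekeeping procedure, plans simultaneous confidence intervals, or says why a single-step rule was chosen.

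**The concern.** A single-step rule holds every outcome to 0.05/3 whatever the other two show. Once the smallest of the three p-values has passed 0.05/3, controlling the family-wise error at 5% no longer requires so strict a threshold for the other two. Holm relaxes it to 0.05/2 for the next p-value and to 0.05 for the largest.

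The trial measures three possible behavioural responses around the same exercise bout, so more than one real effect is plausible. In that case the fixed threshold can miss a real second or third effect that Holm would declare with the same data and the same 5% limit.

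**Working it through.** **Inputs.** From the SAP: overall alpha 0.05, three outcomes, n = 60, 80% power, R squared 20.4%. Not in the documents, so assumed: the number of predictors in the power model, the power of the exercise test for each outcome, and the correlation between outcomes.

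**1. The SAP's own figure.** Take the overall F test of R squared = 0 with k predictors, degrees of freedom k and n − k − 1, and noncentrality n × R²/(1 − R²).
- Noncentrality: 60 × 0.204/0.796 = 15.38.
- With k = 3 (df 3 and 56), power is 79.9% at 0.05/3 and 80.1% at 0.017. The R squared detectable with 80% power is 20.43% and 20.36% respectively.
- k = 1, 2 and 4 give about 15.5%, 18.4% and 22.1%, so k = 3 is inferred.

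The 20.4% therefore reproduces, as power for a whole three-predictor model. It is not power for the exercise effect.

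**2. The same model at Holm's three thresholds.** With k = 3 and R squared 0.204, power is 79.9% at 0.05/3, 84.2% at 0.05/2 and 90.4% at 0.05.

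**3. A case that can be checked by hand.** Assume three real effects, independent two-sided z-tests, and 80% power at 0.05/3.
- Mean of each z: 2.394 + 0.842 = 3.236.
- Chance that one p-value falls below 0.05/3, 0.05/2 and 0.05: 0.800, Φ(3.236 − 2.241) = 0.840, and Φ(3.236 − 1.960) = 0.899.
- Bonferroni, all three detected: 0.800³ = 0.512.
- Holm, all three: (0.840³ − 0.040³) + 3 × 0.059 × (0.840² − 0.040²) = 0.593 + 0.125 = 0.717.
- Holm, exactly two: 3 × 0.101 × (0.840² − 0.040²) = 0.213.
- Holm, exactly one: 3 × 0.800 × 0.160² = 0.061.
- Holm, per outcome: (3 × 0.717 + 2 × 0.213 + 0.061)/3 = 0.88, against 0.80.
- At least one detected: 0.717 + 0.213 + 0.061 = 0.99 for Holm and 1 − 0.200³ = 0.992 for Bonferroni. These are the same, because both methods start at 0.05/3.

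**4. Range over the unknowns.** Simulation, 1,000,000 replicates per scenario, correlation 0, 0.3 and 0.6, equal power for each real effect:

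| Real effects | Bonferroni power per outcome | Holm's gain per outcome |
|---|---|---|
| 3 | 50% | 7–8 points |
| 3 | 80% | 6–8 points |
| 3 | 90% | 4–5 points |
| 3 | 95% | 2–3 points |
| 2 | 50% to 95% | about 1–3 points |
| 1 | 50% to 95% | essentially nil |

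At 80% power with three real effects, the chance of detecting all three by correlation is:

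| Correlation | Bonferroni | Holm |
|---|---|---|
| 0 | 51% | 72% |
| 0.3 | 57% | 74% |
| 0.6 | 63% | 78% |

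A separate simulation of three-predictor regressions at n = 60 and R squared 0.204 (correlation 0 to 0.5) gave similar results: about 80% to 87–88% per outcome, and 51–60% to 73–77% for all three.

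**5. Error.** At 80% power, Holm's family-wise error was at most 4.9% in every scenario with a null outcome. With exactly one null outcome it was about 4%, against 1.7% for Bonferroni.

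**The case against.** **Bonferroni is not an error.** This stands. It controls the family-wise error, the sample-size statement does not change, and the chance of at least one significant outcome is the same under both methods.

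**A reader might infer that Bonferroni gives up power for no benefit at all.** The documents do not support that. Holm gains by spending error that Bonferroni leaves unspent when some outcomes are null (step 5). Bonferroni also has simple matching simultaneous intervals. The SAP relies on neither advantage, but both are real.

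**A reader might take 51% to 72% as the gain to expect.** That is close to the most favourable case: three real, equal, uncorrelated effects at exactly 80% power. The SAP's 80% belongs to a whole regression model, and the SAP expects its mixed models to raise power. Three food-cue measures from the same people in the same session are unlikely to be independent.

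**Holm needs a defined test.** The SAP names exercise and time as random effects and only sex as fixed, and the Protocol schedules two assessments after the bout. No single exercise contrast per outcome is stated. This gap is real, but it does not favour Bonferroni: dividing by three also presumes one test per outcome.

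**A reader might infer that rounding to 0.017 breaks the 5% limit.** Three times 0.017 is 0.051, but the exact fraction is printed beside it and the difference is negligible.

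**Conclusion.** The point holds as an efficiency improvement, not as a fault. Holm's advantage over single-step Bonferroni is a general result that needs no independence assumption: it never rejects less, and its family-wise error stays at or below 5%.

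Only the size of the gain is uncertain. It is worthwhile if all three effects are real and power is moderate, small if two are real or power is already high, and essentially nil if one is real. These sizes assume equal power for each exercise test and correlation between 0 and 0.6, neither of which the documents give. The relaxed thresholds apply after the smallest p-value, not after whichever outcome is listed first.

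**What to change.** Replace the Bonferroni sentence in the SAP with wording such as:

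> One pre-specified exercise test will be made for each of the three response variables. The three p-values will be ordered and tested by Holm's step-down procedure: the smallest against 0.05/3, the next against 0.05/2 and the largest against 0.05, stopping at the first that is not rejected.

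Keep the power statement at 0.05/3 and label it as the first Holm step.

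The change needs no extra participants or data. It has three costs:
- The exercise test for each outcome must be written down. The present rule needs that too.
- Holm has no simple matching simultaneous intervals. If 98.33% intervals are reported (100 × (1 − 0.05/3)), the SAP should say that Holm governs significance and that an interval may include zero for an outcome Holm rejects. With three real effects at 80% power, this happens for at least one outcome in about 16–22% of simulated trials.
- More of the 5% error is used when some outcomes are null: about 4% instead of 1.7% with one null outcome, still within the limit.

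### The crossover analysis names no Visit 2/Visit 3 effect and leaves 'time' undefined, so a shift between visits would inflate the error of a between-visit exercise comparison

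*SAP*

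**What the plan says.** The design is a two-condition crossover. The protocol (Visits 2 and 3) says "The order of the visits will be counterbalanced", and the SAP's power paragraph repeats this: participants are "counterbalanced to start with and without exercise and then crossing over to the other treatment". At each visit the tasks are done "before and twice after an acute bout of either exercise or sedentary activity", so each person contributes 2 × 3 = 6 administrations of each task.

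The SAP gives the model in one sentence: "Linear mixed models will be fit with exercise and time as random effects to account for repeated measures and sex as a fixed effect". Further covariates are limited to the VAS ratings: "VAS scale ratings of hunger/satiety and exercise enjoyment will be assessed and included for adjustment as necessary". The only hint about coding is "With binary explanatory variables, an unstructured covariance matrix for the random effects will be assumed, but alternatives will be considered if needed", which does not say which variables are binary. Neither document names a visit-number, period or sequence term for the analysis, and neither says what 'time' is.

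At Visit 1, enrolled participants "complete a food frequency questionnaire (DHQ-3), be assessed for body composition (BodPod), and have waist circumference measured" and receive an accelerometer. No practice of the food reinforcement, attentional bias or inhibitory control tasks is listed.

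**The concern.** There are two time-like factors: visit (two levels) and assessment within visit (three levels). One term called 'time' cannot carry both. If it means assessment, the visit is unmodelled. If it means visit, the three assessments are unmodelled.

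The first reading matters for the exercise comparison because each person has exercise at one visit and TV at the other. As described, the Visit 2 pre-bout assessment is a participant's first contact with the tasks, so a general change from Visit 2 to Visit 3 through familiarity is plausible, though its size is unknown. Such a change raises the exercise-minus-sedentary difference in one order group and lowers it equally in the other. Counterbalancing makes these cancel in the mean. Unless visit is in the model, they do not cancel in the residual variance. The trial would then have paid for the balance in its design without collecting the precision in its analysis.

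**Working it through.** **The SAP's own power figure.** For the overall F test in linear regression, noncentrality = n·R²/(1 − R²) = 60 × 0.204/0.796 = 15.4, with k and 59 − k degrees of freedom. At alpha 0.017, power is 86.0% for k = 2, 80.1% for k = 3 and 74.7% for k = 4. The stated 80% therefore reproduces with three predictors. The SAP does not give the number; three would match exercise, time and sex. This figure is not disputed.

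**Inputs for the check.** From the SAP: n = 60 and alpha = 0.05/3, here taken as two-sided. Assumed: 30 participants per order (the SAP's 30/30 split is by sex; order is described only as counterbalanced), and a visit shift P in units of the SD of the within-person exercise-minus-sedentary difference D.

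**Model.** D has mean d + P if exercise is at Visit 3 and d − P if it is at Visit 2, with SD 1.

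- Estimate: with 30 per order, the mean of D is d whatever P is. Its true sampling SD is 1/√60 = 0.129.
- With visit modelled: the residual SD is 1 on 58 df. Solving for 80% power gives d = 0.428 (noncentrality 60 × 0.428² ≈ 11.0).
- Without visit: the expected variance of D is 1 + P² × 60/59, so the estimated SE is too large by √(1 + P² × 60/59).
- Power without visit, hand approximation: Φ(d√60 − 2.46 × SE ratio), where d√60 = 3.32 and 2.46 is the critical t on 59 df. At P = 0.5 this is Φ(3.32 − 2.76) = 0.71.

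The table gives simulated power and type I error (100,000 or more trials per setting), which agree with the approximation.

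| Shift P | SE ratio | Power, visit omitted | Power, visit modelled | Type I error, visit omitted |
|---|---|---|---|---|
| 0.1 | 1.005 | 79.5% | 80% | 0.016 |
| 0.2 | 1.02 | 79% | 80% | 0.014 |
| 0.3 | 1.04 | 77% | 80% | 0.013 |
| 0.5 | 1.12 | 71% | 80% | 0.008 |
| 1.0 | 1.42 | 43% | 80% | 0.001 |

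With no shift, the term costs almost nothing: 80.00% with it against 80.04% without.

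**Does a random exercise slope absorb the shift?** No. In a small mixed-model simulation (25 trials per setting, random intercept and random exercise slope, three assessments per visit) with a visit shift of 0.7 outcome units, the SE for exercise averaged 0.136 without a fixed visit term and 0.103 with it.

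**Unequal completion.** No dropout figure is given, so these splits are assumptions. Bias = P × (nA − nB)/(nA + nB). At 30/27 this is 3/57 = 5% of the shift; at 30/24 it is 6/54 = 11%. For P = 0.3 and 30/24 the bias is 0.033 SD. Against an SE of 1/√54 = 0.136 that is a quarter of one SE, and the type I error stays at about 0.016.

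**Change from pre-bout.** Assume a person SD of 1, visit SD 0.3, residual SD 0.6 and effect 0.30, with the mean of the two post-bout values as the post value. The contrast SD is √(2 × 0.36 × 1.5) = 1.04. A shift constant within the visit cancels, and power is 41–42% with or without a visit term. If only the very first administration differs, by 0.4 (0.4/1.04 = 0.38 SD), power is 35% without and 41% with visit modelled in that contrast.

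**The case against.** The strongest reply is that 'time' may already mean visit. Visit 2 against Visit 3 is binary, pre/post 1/post 2 is not, and the SAP speaks of binary explanatory variables. That reading is possible, but it moves the gap rather than closing it: the three assessments within each visit would then have no term.

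Second, read literally, the SAP lists exercise only as a random effect, so it names no fixed exercise contrast whose SE could be inflated. This is fair. The tested contrast is unspecified, and the loss computed here applies only if exercise is compared between visits. It is a reason to name the contrast as well as the visit term.

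Third, with a pre-bout assessment at each visit, change from pre-bout is a natural target, and a shift constant within the visit drops out of it. This also stands, and it limits the point. But the SAP specifies neither a change score nor an exercise-by-time interaction, and a first-administration effect would not cancel.

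Fourth, the size is assumed. The documents give no visit shift, within-person SD or learning effect, and nothing in them supports shifts as large as 0.5 or 1.0 SD. Those rows are illustrative. For shifts up to 0.3 SD the loss is about 3 points or less.

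**Conclusion.** The concern holds as a modest matter of efficiency and clarity. The plan names no explicit visit-number term, 'time' is undefined, and under either reading of it one of the two repeated-measures factors is left out.

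For a between-visit exercise contrast with balanced orders, omitting visit gives a conservative test: no bias, unchanged true sampling error, and a loss that is small for small visit shifts and grows with larger ones. Bias requires unequal completion by order as well, and is small in the cases computed. None of those cases shows added false-positive risk. The sizes rest on the assumed shift, on equal order groups and on the choice of contrast. The SAP's stated 80% power at an R squared of 20.4% is not wrong.

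**What to change.** In the SAP:

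1. Define time as the assessment occasion, with three levels: pre-bout, post 1 and post 2.
2. Add visit number (Visit 2 or Visit 3) as a fixed effect in the models for all three outcomes.
3. State which contrast tests exercise, and include exercise as a fixed effect accordingly. If the target is exercise-by-time, also add visit-by-time.
4. Report the number of completers by visit order.

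A sequence term is optional and is not needed for this point. The cost is a few lines of SAP text and one degree of freedom, or three with visit-by-time (1 + 2). No new data are needed.
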